### **5.3 TOXICITY CRITERIA**

This study will utilize NCI Common Terminology Criteria for Adverse Events (CTCAE) version 3.0, published June 10, 2003, for toxicity and adverse event monitoring and reporting. (Refer to [http://ctep.info.nih.gov/reporting/ctc\\_v30.html](http://ctep.info.nih.gov/reporting/ctc_v30.html)). All clinical treatment areas will have access to a copy of CTCAE version 3.0.

## **6 STATISTICAL CONSIDERATIONS**

### **6.1 OVERALL STATEMENT OF OBJECTIVES**

The primary objective of this study, on which the sample size will be based is to determine the proportion of patients who will generate a specific immune response following vaccination as tested in tetramer, ELISPOT and cytotoxicity assay, and to evaluate if this is adequate for future consideration. Determination of safety of the vaccination is also an important endpoint. It is also of interest to assess risk of progression among patients with metastatic Stage D0 prostate cancer naïve to androgen deprivation therapy vaccinated with these peptides using PSA doubling time as a surrogate marker of this risk.

### **6.2 PRIMARY OBJECTIVE AND STATISTICAL JUSTIFICATION FOR SAMPLE SIZE**

This study will be conducted as a prospective, randomized two arm, pilot trial to explore the utility of TARP peptide vaccination alone or vaccination with TARP peptide-pulsed dendritic cells in patients with Stage D0 prostate cancer.

The primary objective is to obtain a reliable estimate of the immunologic response rate to vaccination with either peptide vaccine or dendritic cells in patients with biochemical progression and to determine if the rate of immunologic response in either arm is adequate to warrant further investigation in subsequent studies. Evaluation of safety and toxicity will also be a primary goal. The study is not designed to have adequate power to identify if one arm is associated with a significantly improved immunologic response rate as compared to the other, as such detection may require very large numbers of patients given the potential similarity of the arms. Furthermore, there is no requirement that only one arm be selected for further development. Should both arms demonstrate adequate immunologic responses, then future studies will consider either or both arms depending on immune responses, feasibility, toxicity and other outcomes such as PSADT.

Patients will initially be screened for HLA-A\*0201 positivity. HLA-A\*0201 patients will then undergo comprehensive protocol eligibility screening and if found to be eligible, will be enrolled in the study. Upon enrollment patients will be randomized in a 1:1 manner to receive TARP peptide vaccination with Montanide® ISA51 VG plus GM-CSF (Arm A) or TARP peptide-pulsed dendritic cells (Arm B).

For each arm, using an acceptable immunologic response rate of 40% ( $p_1=0.40$ ) and an unacceptable rate of 10% ( $P_0=0.10$ ) and using a two-stage optimal design (Simon R, *Controlled Clinical Trials* 10:1-10, 1989) with  $\alpha = 0.05$  and  $\beta = 0.10$ , we will initially accrue 9 patients in each arm. An unacceptable response rate of 10% (or less) and an acceptable response rate of 40% were determined based on historical clinical trial response rates to vaccines and immune-based therapies for cancer. If 0-1 patients develop an immunologic response as defined in Section 5.2.1, then no further patients will be enrolled. If 2 or more of these 9 patients develop an immunologic response, we will accrue 11 additional patients for a maximum total of 20 patients per arm. If 2-4 of 20 has an immunologic response, then the results from this arm will be considered inadequate for further investigation. If 5 or more of these 20 has an immune response, we will be able to conclude that the vaccine on the given arm is worthy of further development in this population on the basis of immune response. Under the null hypothesis ( $p_0=0.20$ ), the probability of early termination is 77%.

There is no requirement that only one arm be selected for further development; should both arms demonstrate adequate immunologic responses, then future studies will consider either or both arms depending on immune responses, feasibility, toxicity and other outcomes such as PSADT.

As stated in Section 3.3.2, an early stopping rule will be used to ensure that the study subjects do not have exposure to excessive toxicity: If more than one of the first nine subjects on a given arm experiences dose limiting toxicity (defined in Section 3.3.1), enrollment will cease for that arm and revisions to the treatment will be discussed with the IRB and FDA. This is because 1/9 has an upper one-sided 90% confidence interval limit of 37%, while 2/9 has an upper one-sided 90% confidence interval limit of 49%; the former would be marginally acceptable as a rate of toxicity while the latter is not. In addition, any unusually severe toxicity noted may result in temporary suspension of accrual pending re-evaluation of the agent. All toxicities noted will be tabulated by type and grade, for each arm. Any such toxicities that appear in at least 5 patients on either arm will also have the distribution of grades of that toxicity compared between the arms using an exact Cochran-Armitage test.

The percent of patients who meet PSADT response criteria as outlined in section 5.2.2 will also be evaluated as a secondary endpoint. In addition, exploratory comparisons of PSADT among study time points will be performed as outlined in Sections 3.1 and 5.2.2. Given that there will be 6 separate comparisons of PSADT, we will only report differences with  $p < 0.01$  as being statistically significant while other differences with  $0.01 < p < 0.05$  will be considered to be trends. Appropriate 95% confidence intervals will be constructed and reported which takes into consideration the two-arm nature of the design. No formal comparison will be undertaken since the study does not have adequate power to address this comparison properly.

It is expected that 1-2 patients per month may be enrolled onto this study. Based on accrual of 18-20 patients per year, accrual should be completed in approximately 2 to 2.5 years if all 40 patients were to be required. To allow for the possibility of inevaluable patients, an accrual ceiling of 43 will be used.

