#### 1.1.2 Secondary Objectives

- 1.1.2.1 Determine the effect of TARP peptide vaccination on serum prostate specific antigen doubling time (PSADT).
- 1.1.2.2 Determine the effect of TARP peptide vaccination on PSA growth rate and regression rate constants.

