## **2 ELIGIBILITY ASSESSMENT AND ENROLLMENT**

### **2.1 ELIGIBILITY CRITERIA**

#### **2.1.1 Inclusion Criteria**

- 2.1.1.1 Males  $\geq$  18 years of age with histologically confirmed adenocarcinoma of the prostate.
- 2.1.1.2 HLA-A\*201 positive
- 2.1.1.3 Patients must have
  - 2.1.1.3.1 Completed and recovered from all prior definitive therapy (surgery, brachytherapy, cryotherapy or radiotherapy) for the primary tumor, or other definitive-intent local therapy.
  - 2.1.1.3.2 Stage D0 disease with documented biochemical progression documented by a rising PSA.
  - 2.1.1.3.3 No evidence of metastatic disease by physical examination, CT scan or bone scan.
  - 2.1.1.3.4 For patients following definitive radiation therapy or cryotherapy: a rise in PSA of  $>2$  ng/mL above the nadir (per RTOG-ASTRO consensus criteria).
  - 2.1.1.3.5 For patients following radical prostatectomy: 2 absolute PSA values  $> 0.3$  ng/mL (per NCCN guidelines)
  - 2.1.1.3.6 Non-castrate level of testosterone:  $\geq 50$  ng/dL (prior ADT allowed; must be  $\geq 6$  months since last dose of ADT).
  - 2.1.1.3.7 A Pre-Enrollment/Baseline PSADT  $> 3$  months and  $\leq 15$  months
    - 2.1.1.3.7.1 Patients must have  $\geq 3$  PSA measurements over  $\geq 3$  months
    - 2.1.1.3.7.2 The interval between PSA measurements must be  $\geq 4$  weeks
    - 2.1.1.3.7.3 For patients receiving 5-alpha reductase inhibitors (5ARI) e.g. finasteride or dutasteride, only PSA values obtained after at least 3 months on therapy may be used to calculate PSADT.
  - 2.1.1.3.8 Performance Status: ECOG 0-2 or Karnofsky 70-100%
  - 2.1.1.3.9 Life expectancy  $\geq 1$  year.
  - 2.1.1.3.10 Hemoglobin  $\geq 10.0$  gm/dL, WBC  $\geq 2,500/\text{mm}^3$ , ALC  $\geq 500/\text{mm}^3$ , ANC  $\geq 1,000/\text{mm}^3$ , platelet count  $\geq 100,000/\text{mm}^3$ .

- 2.1.1.3.11 PT/PTT  $\leq$  1.5X ULN unless receiving clinically indicated anticoagulant therapy.
- 2.1.1.3.12 SGOT/SGPT  $\leq$  2.5X ULN, total bilirubin  $\leq$  1.5X ULN, Cr  $\leq$  1.5X ULN, estimated GFR (eGFR)  $>$  60 ml/min.
- 2.1.1.4 Hepatitis B and C negative, unless the result is consistent with prior vaccination or prior infection with full recovery.
- 2.1.1.5 HIV negative
- 2.1.1.6 No use of investigational agents within 4 weeks of study enrollment.

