## **3 STUDY IMPLEMENTATION**

### **3.1 STUDY DESIGN**

This is a randomized, prospective pilot study of TARP peptide vaccination in HLA-A\*201 patients with Stage D0 prostate cancer. HLA-A\*201 positive eligible patients with *no evidence*

of brain, visceral or bony metastatic disease, a non-castrate testosterone level  $\geq 50$  ng/dL (prior ADT allowed; must be  $\geq 6$  months since last dose of ADT), and a PSADT  $> 3$  months and  $\leq 15$  months will be randomized to receive TARP peptides with Montanide® ISA 51 VG adjuvant plus GM-CSF administered by deep subcutaneous (SC) injection or autologous, TARP peptide-pulsed dendritic cells administered intradermally (ID).

TARP peptides or TARP-pulsed dendritic cells will be administered every three weeks at weeks 3, 6, 9, 12, and 15 for a total of five vaccinations with a booster dose of TARP vaccine given at Weeks 48 and 96. PSADT will be calculated in months at the following study time points: Pre-Enrollment/Baseline, weeks 12, 24, 36, 48, 60, 72, 84, 96, 108, 120, 132, and 144. PSADT will be calculated using the Memorial Sloan-Kettering Cancer Center cancer information prostate nomogram for PSA doubling time found at:

<http://www.mskcc.org/mskcc/shared/forms/Nomograms/flash/load.cfm?type=Prostate&width=586&height=505&title=Prostate%20Nomogram> as recommended in the Prostate Specific Antigen Working Group Guidelines. Cumulative PSA values within 12 months inclusive of the study time point will be used for calculation of the baseline/Week 0 PSADT.

Exploratory comparisons of percent change in PSADT will be done among the following time points:

[figure not shown]
- Pre-Enrollment/Baseline PSADT vs. Week 12 PSADT
- Pre-Enrollment/Baseline PSADT vs. Week 24 PSADT
- Pre-Enrollment/Baseline PSADT vs. Week 36 PSADT
- Pre-Enrollment/Baseline PSADT vs. Week 48 PSADT
- Week 24 PSADT vs. Week 36 PSADT
- Week 36 PSADT vs. Week 48 PSADT
- Additional exploratory analyses of PSADT will be performed of Pre-Enrollment/Baseline PSADT vs. Weeks 60, 72 and 96 and Week 48 PSADT vs. Weeks 96, 108 and 144 PSADT.

Week 24 PSADT responders will be allowed to receive an additional dose of TARP peptide vaccine at Week 36. All patients will receive a booster of vaccine at Weeks 48 and 96.

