### 5.2.2 PSADT Response Criteria

PSADT was chosen as a surrogate marker for biochemical response to vaccination based on the Prostate-Specific Antigen Working Group's consensus Guidelines on PSADT. Utilization of PSADT as a predictive factor of disease progression and prostate cancer death is based on level II evidence derived from cohort- or case-controlled analytic studies or controlled, non-randomized trials that have been validated in multiple data sets, PSADT will be calculated using the Memorial Sloan-Kettering Cancer Center cancer information prostate nomogram for PSA doubling time found at:

<http://www.mskcc.org/mskcc/shared/forms/Nomograms/flash/load.cfm?type=Prostate&width=586&height=505&title=Prostate%20Nomogram> recommended in the Prostate Specific Antigen Working Group Guidelines. The PSADT is calculated assuming an exponential increase in serum PSA and first order kinetics. The formula takes into account the natural logarithm of 2 divided by the slope obtained from fitting a linear regression of the natural log of PSA on time. All PSA values used in the calculation should be 0.20 ng/ml or greater and follow an increasing trend. PSA values need not be consecutively increasing and all values obtained during a maximum period of 12 months prior to a given protocol time point will be included in the calculation. The maximum period of the last 12 months is recommended to reflect current disease activity because in some men PSADT may change over time. Multiple studies concur that men with a PSADT < 3 months are at extremely high risk for metastatic disease progression

and death with prostate cancer mortality approaching 100%; for this reason they have been excluded from participation in this study. In contrast, men with a slow PSADT i.e. > 15 months have an extremely low risk of death from prostate cancer.

The following general guidelines regarding PSA determinations and calculation of PSADT used in this protocol will be adhered to (refer to [Appendix 5](#), PSADT Calculation Guidelines)

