#### **Pre-Enrollment/Baseline and On Study PSADT:**

- PSADT will be calculated using the Memorial Sloan-Kettering Cancer Center cancer information prostate nomogram for PSA doubling time found at:  
<http://www.mskcc.org/mskcc/shared/forms/Nomograms/flash/load.cfm?type=Prostate&width=586&height=505&title=Prostate%20Nomogram>
- Minimum requirements for PSADT include  $\geq 3$  PSA measurements over  $\geq 3$  months.
- The interval between PSA measurements must be  $\geq 4$  weeks.
- For patients receiving 5-alpha reductase inhibitors (5ARI) e.g. finasteride or dutasteride, only PSA values obtained after at least 3 months on therapy may be used to calculate PSADT.
- Calculated PSADT values will be reported in months
- The same laboratory must have performed PSA values used in the calculation of PSADT.
- All PSA values used in the calculation should be  $\geq 0.20$  ng/mL and follow a rising trend although all values need not be consecutively rising.
- All values obtained over a maximum period of 12 months prior to any given protocol time point assessment should be included in the PSADT calculation to reflect the patient's current disease activity.
- PSA values obtained within  $\leq 2$  weeks of instrumentation, documented infection (prostatitis), or radiation proctopathy should be *omitted* from inclusion in PSADT calculations.

On Study PSADT will be calculated at baseline and weeks 12, 24, 36, 48, 60, 72, 84, 96, 108, 120, 132, and 144.

Exploratory comparisons of percent change in PSADT will be done among the following time points:

- Pre-Enrollment/Baseline PSADT vs. Week 3-12 PSADT/
- Pre-Enrollment/Baseline PSADT vs. Week 24 PSADT
- Pre-Enrollment/Baseline PSADT vs. Week 36 PSADT
- Pre-Enrollment/Baseline PSADT vs. Week 48 PSADT
- Week 24 PSADT vs. Week 36 PSADT
- Week 36 PSADT vs. Week 48 PSADT
- Additional exploratory analyses of PSADT will be performed of Pre-Enrollment/Baseline PSADT vs. Weeks 60, 72 and 96 and Week 48 PSADT vs. Weeks 96, 108 and 144 PSADT.

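### The PSADT that qualifies a man for entry is also his baseline, so regression to the mean can lengthen PSADT with no vaccine effect, and the p<0.01 label on baseline contrasts does not hold its nominal error

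*Combined protocol and SAP*

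**What the plan says.** Section 2.1.1 admits men on "A Pre-Enrollment/Baseline PSADT $> 3$ months and $\leq 15$ months". Section 5.2.2 sets the data behind it: "Minimum requirements for PSADT include $\geq 3$ PSA measurements over $\geq 3$ months". The estimator is the "natural logarithm of 2 divided by the slope obtained from fitting a linear regression of the natural log of PSA on time".

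Section 3.1 builds the baseline from the same period: "Cumulative PSA values within 12 months inclusive of the study time point will be used for calculation of the baseline/Week 0 PSADT". Entry criterion and baseline thus share both a name and their PSA values.

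Sections 3.1 and 5.2.2 list six main comparisons. Four use the baseline (weeks 12, 24, 36 and 48), for example "Pre-Enrollment/Baseline PSADT vs. Week 24 PSADT". The other two are week 24 against 36 and week 36 against 48. Baseline against weeks 60, 72 and 96 is additional.

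Section 6.2 states that "exploratory comparisons of PSADT among study time points will be performed as outlined in Sections 3.1 and 5.2.2". It calls p<0.01 statistically significant and p between 0.01 and 0.05 a trend, and the only reason it gives for the threshold is that there are six comparisons. Neither the test nor its sidedness is named. A secondary objective in Section 1.1.2 is: "Determine the effect of TARP peptide vaccination on serum prostate specific antigen doubling time (PSADT". Both randomised arms are vaccinated. Sections 3.1, 5.2.2 and 6.2 mention no run-in, separate baseline or regression to the mean.

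**The concern.** A fitted slope from a few PSAs is noisy. Near the 15-month cut, men whose slope came out high by chance are admitted and men whose slope came out low by chance are not. Among those admitted, the measured baseline slope is on average steeper than the true one. Later windows are not selected in this way, so the average slope falls and PSADT lengthens even if the vaccine does nothing. The effect is present on the ln PSA slope scale, so changing the scale does not remove it. A stricter threshold does not correct a bias, and a larger sample makes a biased test more likely to reject.

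At stake is the secondary objective on PSADT. Section 6.2 also lists PSADT among the outcomes that may inform which arm or arms go forward. With no unvaccinated group, nothing in the planned comparisons would separate this drift from a vaccine effect.

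**Working it through.** **The plan's own figure.** The threshold of 0.01 is justified by six comparisons. If these were independent, the familywise error would be 1 − 0.99^6 = 5.9%, so the threshold does its stated job, provided each test has the error it claims. The plan gives no SD, sample size or power for PSADT. The available n is up to 20 per arm (Section 6.2), or 40 pooled.

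**Slope noise against the entry cut.** A PSADT of 15 months is a slope of ln 2/15 = 0.0462 per month; 3 months is 0.231. The SE of a least-squares slope is σ/√Σ(t − t̄)². Assume an ln PSA error SD σ = 0.10 and equal spacing:

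| Baseline PSAs | Σ(t − t̄)² | SE of slope per month |
|---|---|---|
| 3 over 3 months (protocol minimum) | 4.5 | 0.047 |
| 4 over 6 months | 20 | 0.022 |
| 5 over 12 months | 90 | 0.011 |

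At the protocol minimum, the SE is as large as the slope at the 15-month cut. With five values over a year it is about a quarter of it (0.011/0.046).

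**No-effect simulation.** Assumptions not in the documents: true PSADT among screened men is lognormal with median 10 months and log SD 0.7; each man's slope is constant; σ = 0.10. From the documents: entry at measured PSADT >3 and ≤15 months, the same values kept as baseline, and the Appendix 5 on-study window of weeks 3, 6, 9, 12, 15, 18 and 24. The test is a paired t on slope, two-sided at 0.01 (assumed), so 0.5% is nominal for lengthening.

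| Baseline PSAs | False lengthening, n=20 | n=40 |
|---|---|---|
| 3 over 3 months | 15% | 37% |
| 4 over 6 months | about 3% | about 6% |
| 5 over 12 months | about 1% | about 1% |

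In the first row the mean slope falls from 0.110 to 0.0925 per month (−16%), and median PSADT goes from 6.8 to 8.1 months.

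**Sensitivity, 3 PSAs over 3 months.**
- Source median 15 months, σ = 0.15: about 60% (n=20) and 95% (n=40).
- Source median 4 to 5 months, σ = 0.10: near nominal, because the lower cut pulls the other way.
- Central case with the 12-month look-back of Section 5.2.2 in place of the weeks 3 to 24 window, n=20: 18% to 21% at week 24 and 23% to 28% at week 48, depending on the test. Sharing pre-study values does not remove the problem.
- Central case with weeks 0 and 3 added to the baseline, as one Appendix 5 window does: 15% falls to about 3% to 4% (n=20), and 37% to about 8% to 9% (n=40).
- Central case after removing men who meet the off-study criterion of a PSADT decrease of 50% or more: 28% (n=20) and 67% (n=40).
- Central case with a signed-rank test on PSADT: 20% (n=20) and 51% (n=40). Part of that excess is skew of ln 2/slope rather than selection, so the t test on slope is the cleaner guide.

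**Contrasts between on-study windows.** With a 52-week look-back, the week 24, 36 and 48 windows reach back to weeks −28, −16 and −4 (24 − 52, 36 − 52, 48 − 52). The two contrasts that do not use baseline can therefore still contain qualifying PSAs. Weeks 3 to 24 against weeks 24 to 48, using post-enrolment values only, gave 0.3% to 0.7% false lengthening in every scenario run.

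**The case against.** The strongest case against is that the size is unknown and could be small. Section 5.2.2 requires all values from the prior 12 months, from one laboratory. If most men bring five PSAs over a year, the error is about 1%. The documents do not say how many men bring, nor what PSADT distribution the screened men have. This stands, and it limits the point to what can happen under permitted data.

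A reader might infer that selection alone must lengthen PSADT, so that the secondary objective would be answered yes whatever the vaccine does. The documents do not support that. The lower cut at 3 months works in the opposite direction, and a fast-progressing source population gives near-nominal error with slight reversal in some settings. Nor should the n=40 rates be read as the plan's error: the plan does not say that the arms are pooled, and per-arm rates are lower.

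Appendix 5 also tabulates a window from 12 months before entry to week 3. It would lessen the bias, but neither Section 3.1 nor Section 6.2 makes it the comparator. Section 3.4.2 lists a PSA at week 0. If that value came after eligibility was settled and entered the baseline, it would dilute the bias too, though less than adding weeks 0 and 3 together.

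Finally, the comparisons are called exploratory and the go/no-go rule rests on immune response. That lowers the stakes but does not justify a significance label with the wrong error rate. Randomisation protects a between-arm contrast, but Section 6.2 plans no formal one, and with both arms vaccinated it would not isolate a vaccine effect.

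**Conclusion.** The point holds in conditional form. The measured PSADT is both the entry filter and the comparator in four of the six listed contrasts, and in the additional ones at weeks 60, 72 and 96. The p<0.01 label on the baseline contrasts therefore does not guarantee its nominal error, and the secondary objective could, though not necessarily would, be answered yes by selection.

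Against a nominal 0.5%, false lengthening runs from near nominal (five PSAs over twelve months, or a source median of 4 to 5 months) through 15% (n=20) and 37% (n=40) in the central case at the protocol minimum, to about 60% and 95% with a source median of 15 months and error SD 0.15. PSA noise, source distribution and PSAs per man are all assumed. The mechanism comes from the documents; the size does not.

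**What to change.** In Section 6.2:

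1. Report baseline-versus-on-study PSADT changes as estimates with 95% confidence intervals, without significance or trend labels. State that estimates and intervals alike include regression to the mean from the entry cut.
2. As a sensitivity analysis, repeat these contrasts with the Appendix 5 window from 12 months before entry to week 3 as comparator. State that this reduces the bias but does not remove it.
3. Keep the p<0.01 label only for contrasts whose two windows use post-enrolment PSA values alone, such as weeks 3 to 24 against weeks 24 to 48. State that both windows follow the first vaccination, so these contrasts do not estimate the effect against baseline.
4. If a simulated no-effect reference is shown, state its assumed source PSADT distribution and give a range. Enrolled men's PSA dates, residual SD and the entry cut do not determine it.

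The cost is SAP wording and one repeated analysis on data already collected. The downside is that the exploratory baseline contrasts lose their p-value labels.

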HIV Serology								
Hepatitis B Serology								
Hepatitis C Serology								
HTLV-1 Serology								
VDRL								
EKG								
CT Scan /Chest/Abd/Pelvis				X				X
Bone Scan				X				X
Lymphocyte Subsets	X			X				X
Anti-TARP Antibody	X			X				X
NKT Cell Assessment								
Tetramer Staining	X	X	X	X	X	X		X
IFN-γ ELISPOT	X	X	X	X	X	X		X
 Cr CTL Assay#	X	X	X	X	X	X		X
PBMCs for Storage	X	X	X	X	X	X		X
Serum for Storage	X	X	X	X	X	X		X

Notes:

- Screening CT scans of the Chest/Abd/Pelvis and Bone Scans may be performed up to 8 weeks prior to enrollment and at outside institutions.
- All on study assessments can be obtained within +/- one week of scheduled measurement to allow for holidays and unscheduled delays.
- Screening for HLA-A\*0201 positivity will be completed before protocol eligibility screening is initiated. Only HLA-A\*0201 positive patients are brought to NIH for further screening and eligibility assessment.
- FluMist™ vaccination will be given with the seasonal influenza preparation when it is available at the time of enrollment.
- X\*: a 6th dose of TARP peptide vaccine will be administered to those patients with a ≥ 50% increase in PSADT at week 24 or who have confirmed immunologic responses to vaccination by tetramer or IFN-g ELISPOT assays as outlined in Section 5.2.1 Immunologic Response Criteria. A booster dose of TARP peptide vaccine will be administered to all patients at Week 48 and 96 who elect to continue on the extension phase of the study through Week 144..
- #: Cr CTL Assay will be performed at the time points indicated only in those patients with evidence of immunologic reactivity by tetramer staining and/or IFN-γ ELISPOT assays.

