### **IFN- $\gamma$ ELISPOT Assay (All Patients)**

Lymphocytes will be separated from heparinized blood using density gradient centrifugation and then be placed in human AB serum with 10% DMSO for storage in liquid nitrogen. At week 24, samples from weeks 0, 12, 18 and 24 will be assessed concurrently utilizing the ELISPOT assay. The ELISPOT measures the number of IFN- $\gamma$  cells and will be used for determination of CTL precursor frequency to TARP peptides in both pre- and post-vaccination peripheral blood mononuclear cells (PBMC). Additional ELISPOT assays will be preformed using samples from weeks 0, 24 and 48 as well as extension year (48-96 and 96-144) timepoints.

Briefly, 96-well MultiScreenTM -HA (nitrocellulose) plates are coated with capture mAb against human IFN- $\gamma$  overnight at RT. Effectors will be thawed and cultured overnight in RPMI 1640 plus 10% human AB serum. Plates are washed and blocked for 2 h with RPMI 1640 plus 10% human AB serum. C1R.A2, antigen presenting cells (APC), are irradiated with 20,000 rad and pulsed for 2 h at 37°C with either TARP peptide, Flu matrix peptide, a negative control peptide (TAX peptide) or a positive control peptide (CEF peptide pool- see notes below). Non-pulsed C1R.A2 APC will be incubated in tandem and will serve as a negative control.  $1 \times 10^5$  PBMC are added to each well followed by pulsed- or non-pulsed C1R.A2 cells at an effector:APC ratio of 1:1. Each sample is run in six replicates to control for variability. HLA-A2 binding Flu matrix peptide 59-66 serves as a positive control for inherent cellular reactivity. In addition, PBMC from two "normal" HLA-A2-positive individuals with previously determined levels of FMP- or CMV-peptide T-cell precursors are run as assay controls. Cells are incubated for 24h and lysed with phosphate buffered saline (PBS)-Tween (.05%). Biotinylated antihuman IFN- $\gamma$

antibody in PBS-Tween containing 1% bovine serum albumin (BSA) is added and the plates are incubated overnight at 4°C. Plates are then washed and incubated with streptavidin-alkaline phosphatase for 2 h at RT. Spots are visualized with BCIP-NBT substrate and subjected to automated evaluation using the ImmunoSpot Imaging system (Cellular Technology LTd, Cleveland, OH). ELISPOT assays will be performed by the Laboratory of Cell Mediated Immunity ([name]) at NCI Frederick.

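### Section 6.2 rests its p < 0.01 rule for PSADT on six comparisons, but the sections it cites each list twelve, and the rule's scope is not stated

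*Combined protocol and SAP*

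**What the plan says.** Section 6.2 states that "exploratory comparisons of PSADT among study time points will be performed as outlined in Sections 3.1 and 5.2.2". The next sentence gives the labelling rule: "Given that there will be 6 separate comparisons of PSADT, we will only report differences with" p < 0.01 as statistically significant, with differences between 0.01 and 0.05 called trends.

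Section 3.1 introduces its list with "Exploratory comparisons of percent change in PSADT will be done among the following time points". Six bullets follow, each naming one pair. The first is "Pre-Enrollment/Baseline PSADT vs. Week 12 PSADT"; the others are baseline against weeks 24, 36 and 48, week 24 against week 36, and week 36 against week 48. A seventh bullet under the same introduction adds what it calls additional exploratory analyses: "Pre-Enrollment/Baseline PSADT vs. Weeks 60, 72 and 96 and Week 48 PSADT vs. Weeks 96, 108 and 144 PSADT".

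Section 5.2.2 has the same structure: six single-pair bullets, none going past week 48, and a closing bullet that begins "Additional exploratory analyses of PSADT will be performed of Pre-Enrollment/Baseline PSADT vs. Weeks 60, 72 and 96" and adds the same week 48 comparisons.

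Elsewhere the later period is treated as an extension. The notes to Appendix 1 speak of patients "who elect to continue on the extension phase of the study through Week 144", and Appendix 4 refers to "extension year (48-96 and 96-144) timepoints".

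**The concern.** The threshold is tied explicitly to a number of comparisons, and that number is half of what the cited sections contain. Section 6.2 points to both sections whole and singles out no sub-list. Its wording covers PSADT differences generally.

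The practical question is how to label an extension result. Suppose baseline against week 96 gives p = 0.008, or week 48 against week 144 gives p = 0.03. On the plain wording the first is significant and the second a trend, yet the stated reason for the cut-off did not count either of them. If the rule was meant to stop at week 48, nothing says so, and nothing says how the later comparisons are to be labelled. The choice is left until results are in hand.

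The stake is modest but real. The effect on PSADT is a stated secondary objective, and Section 6.2 names PSADT among the outcomes that may inform which arm or arms go forward. No p-value formally drives that decision, but a loosely assigned label could colour it.

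**Working it through.** **Inputs.** From Section 6.2: stated count 6; significant if p < 0.01; trend if p lies between 0.01 and 0.05. From Sections 3.1 and 5.2.2: the lists of pairs.

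**Step 1: reproduce the plan's count.** Taking only the single-pair bullets: baseline against weeks 12, 24, 36 and 48 (4), plus 24 against 36 and 36 against 48 (2), gives 4 + 2 = 6. The stated figure is recovered.

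**Step 2: count everything in the cited sections.** The closing bullet adds baseline against weeks 60, 72 and 96 (3), and week 48 against weeks 96, 108 and 144 (3), so 3 + 3 = 6 more. None repeats an earlier pair. Total: 6 + 6 = 12 in each section.

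**Step 3: consequence for false labels.** Assume every null is true and one test per comparison. For k comparisons:

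- expected false significant labels = 0.01 × k
- upper bound on the chance of at least one = 0.01 × k, whatever the correlation
- the same chance under independence = 1 − 0.99^k
- expected false trend labels = (0.05 − 0.01) × k = 0.04 × k

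| | k = 6 | k = 12 |
|---|---|---|
| Expected false significant labels | 0.06 | 0.12 |
| Upper bound, at least one | 6% | 12% |
| Under independence, at least one | 5.9% | 11.4% |
| Expected false trend labels | 0.24 | 0.48 |

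The independence row is only illustrative. PSADT values come from the same patients and use PSA values from up to the previous 12 months, so the comparisons are correlated. The bounds do not depend on this.

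**Step 4: sensitivity to an unstated choice.** The plan does not say whether the arms are pooled for these tests. If each arm were tested separately, the numbers of tests would be 12 and 24, and the expected false significant labels 0.12 and 0.24. The ratio of two between the readings is unchanged.

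**Step 5: is 0.01 a formal correction?** 0.05/6 = 0.0083, which rounds to 0.01 but does not equal it; 0.05/5 = 0.01 would correspond to five tests. The plan names no correction method, so 0.01 is best read as a convention chosen with six comparisons in mind.

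**The case against.** The best defence is that the six is right for what it counts. It reproduces exactly from the six single-pair bullets, and the protocol itself sets the remaining pairs apart as additional. That stands: a reader might infer a miscount, and the documents do not support that reading. The fault is a mismatch of scope between Section 6.2 and the sections it cites. The defence does not close the gap, because the first six pairs are also headed exploratory, both groups sit under one introduction, and no sentence confines the rule to the first.

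A reader might also infer that the extension comparisons have no rule at all. That is too strong: the general wording of Section 6.2 can be applied to them. What is missing is an explicit statement either way.

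A third defence is that the later pairs are purely descriptive. No text says so. The Appendix 5 worksheet intended for statistical analysis includes windows after week 48 with a percent-change column. Those are windows and not the same pairs, but they show that extension PSADT data are meant to be analysed.

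Finally, Section 6.2 says that no formal comparison will be made for want of power. That sentence follows a reference to the two-arm design and echoes the earlier statement about power between arms, so it is most naturally read as between-arm. Read otherwise, it would cancel the p < 0.01 rule in the same paragraph.

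The point that these are exploratory analyses of a secondary endpoint is fair, and it limits the importance of the finding.

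**Conclusion.** This is an internal inconsistency of minor consequence that should be corrected. The threshold is justified by six comparisons, but as worded it can be applied to twelve. If it is, the bound on the chance of any false significant label rises from 6% to 12%, and the expected number of false trend labels from 0.24 to 0.48. These figures assume that all nulls are true and that each comparison is tested once.

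Two stronger conclusions should not be drawn. The plan breaks no promised error rate, because it states no family-wise target. Nor do the documents show that the threshold ought to be recalculated for twelve tests: no correction method is named, and the number of tests also depends on whether the arms are pooled, which is not stated.

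It is plausible that the count was written before the extension comparisons were added, or was meant to leave them out. The documents do not say which. The primary immunologic endpoint, the sample size, the two-stage rule and the toxicity stopping rule do not use these p-values and are unaffected.

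**What to change.** Add one sentence to Section 6.2 stating that the p < 0.01 criterion and the trend label apply only to the six named comparisons through week 48. State there also that the six extension comparisons (baseline against weeks 60, 72 and 96; week 48 against weeks 96, 108 and 144) will be reported with 95% confidence intervals and without either label. The existing count and threshold then agree and need no change.

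This needs no new data and no change to the design. The cost is that some exploratory extension results can no longer be called significant or a trend.
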